3.2 Secondary Objective(S)

Mixed methods evaluation of staff experiences of using the tool and the mitigation approaches that are recommended (based on analysis of acceptability by staff and feasibility of implementation).

3.3 Outcome measures/endpoints

Primary measures/endpoint:

- Average number of aerosol droplets per minute per clinical encounter as measured by an air particle counter (APC) installed next to the clinician and at up to 4 other fixed locations in the room or ward bay. (A clinical encounter is defined as *one* outpatient consultation, AGP procedure or ward session.)

Secondary measures/endpoint:

- Normalisation Measure Development Questionnaire (NoMAD)
- Ethnographic observations using formal and informal interviews to explore practitioners' views on the importance of AISaT, usability, management of the AISaT software and challenges to fidelity in implementation, and how team members can work together effectively to support implementation
- An estimation of the cost efficiency of AISaT

4. TRIAL DESIGN

[figure not shown]

Figure 1. Schematic diagram of overall trial design

The trial will be run in a staged way as a series of crossover randomised control trials (RCTs) in 2 hospitals, each trial stage being in a different clinical location, preceded by a pilot phase. The locations are in increasingly complex areas. The first location will be an outpatient consulting room. The second will be in a room where aerosol generating procedures (AGP) are performed, e.g. in endoscopy or in Ear Nose and Throat (ENT), and the third will be inpatient ward bays. **Randomisation will be by clinician, not patient.** The order in which the clinicians receive each intervention is determined at random.

Pilot Phase

Before each RCTs commence, a **pilot phase** will identify the optimal settings to use in each setting. The pilots will happen first in consulting rooms during clinics with doctors and patients present. Aerosol droplet generation will be determined using 2 different approaches, to confirm work that has been previously done in a laboratory setting: (a) simply relying on aerosol droplets generated by the doctor-patient clinical interaction in the room; (b) using a 'breathing' robot that we have already developed which generates pre-defined levels of aerosolised saline (salt water).³¹ Up to 4 different sets of conditions will be tested (saline solution at 3 rates of aerosolisation, 1 with only aerosol droplets generated by humans) during routine clinical interactions to determine the optimum approach to achieve the trial endpoints. Air particle counters (APCs) will be installed next to the clinician. We will measure the number of aerosol droplets on average per minute per clinical encounter as measured by an air particle counter (APC) installed next to the clinician and other fixed locations in the room or ward bay. We will perform each set of conditions three times to confirm reproducibility. In total, a maximum of 12 clinic sessions will be included in consulting rooms in the pilot phase. Prior to the second and third clinical trial phases, optimum conditions will again be tested in aerosol generating procedure (AGP) rooms and ward bays where further changes may be needed. It is envisaged that no more than 9 AGP sessions, which are usually half days, and 3 full ward days (up to 24 hour periods, although it is likely that studies can be concluded within a few hours) will be needed to achieve this.

The pilot phases will be informed by initial work on understanding the perspectives of staff and patients in relation to the intervention. This will consist of the following work:

To explore the perspectives of national expert building engineering and infection control leads, management leads, clinical and estates staff, patients and the public we will conduct

- i. *Ethnographic observations*, and informal interviews with, infection control leads, clinical and estates staff to consider use of ventilation devices, how they are deployed, how are they used, challenges and solutions to their use.
- ii. Up to 15 *semi-structured interviews* designed according to key tenets of NPT with management leads, clinical and estates staff. We will develop an understanding of views on critical issues, such as:
 - a. the importance of a focus on reducing transmission of viral illnesses
 - b. challenges hospitals might face reducing transmission
 - c. strategies already implemented to reduce transmission (including aerosol-based transmission)
 - d. likely acceptability and use of an AI solution to this issue. In what circumstances would they use such technology and what would we need to do to encourage use.
 - e. A key part of this work will be to identify affordable retrofit approaches that our Air Safety Tool (AISaT) software should be able to assess to bring both maximum utility and uptake in clinical settings.

The study will also involve usability testing of the AISaT: We will carry out a rapid qualitative study with staff to capture their views on the new tool and how it can be integrated into normal clinical

workflows and pathways. Staff will have the opportunity to test the tool and reflect on their experiences through a series of “Think Aloud” interviews (a common approach used in the usability testing of technological innovations). The researchers will observe the members of staff as they use the tool and will use questions in a pre-established interview topic guide to engage staff members in verbalising their thoughts as they are using the tool. The researcher will also carry out observations as the member of staff uses the tool and will record these in the form of fieldnotes. The research team will rely on regular feedback loops to share emerging findings from the usability testing with the clinical trial implementation team, and with the engineering team to refine the tool. Successive iterations of the AISaT software will be presented to an existing patient advisory group and professional stakeholder panel, to explore perceptions of members, ensure that development in the next period aligns with patient needs and to optimise the user interface.

Randomised Controlled Trial (RCT) Stages

Each **RCT stage** will be run in a cross-over format with aerosol droplet generation determined by the outcomes of the pilot phase.

The first two RCT stages will involve hospital clinicians at each hospital running a weekly session in the same clinic or AGP rooms. Each clinician will be involved for 3 weeks. There will be different configurations each week to allow direct comparison. The AISaT will be turned on and air quality safety measures will be implemented (including the use of air filters, screens, fans etc.), turned off completely with no extra air quality safety measures or air quality safety measures given to the clinician to use and place as they choose. The weekly order of these 3 different configurations will be randomised. These 3 segments of the trial will each be conducted over 3 consecutive weeks.

Fifty four clinicians and their patients will be invited to join, equating to roughly 27 clinicians per hospital. All patients attending either their outpatient clinic appointment or their AGP will be invited to join. Educational material will be made available in multiple languages to encourage broad participation from patients.

As these are cross-over trials, each clinician will be their own control.

Air particle counters (APCs) will be installed next to participating clinicians and at up to 4 other fixed locations in the room or ward bay, to measure the average number of aerosol droplets per minute per clinical encounter. A clinical encounter is defined as *one* outpatient consultation, AGP procedure or ward session. A small aerosol-producing device(s) may also be installed within the room, if needed, as determined in the pilot phase.

To assess numbers of people in the rooms and amount of movement (each of which will impact airflows and infective respiratory particle numbers) an infrared camera will be used throughout to generate video heatmaps (figure 2). The camera will detect heat emanating from people in the room but will not be able to identify any individual person.

[figure not shown]

Figure 2. A heatmap of 2 people sitting on a park bench. Whilst it is possible to locate them precisely, it is not possible to identify them.

For the trial in the 3rd environment (in the ward bays with approximately 6 beds), the trial will be run on 3 consecutive days. As with the other 2 stages, the configurations will be different on each day, to allow direct comparisons. The AISaT will be turned on and air quality safety measures will be implemented, turned off completely with no extra air quality safety measures or air quality safety devices (such as filters, fans and screens etc.) given to the senior nurse on the ward to use and place as they see fit. The daily order of these 3 different configurations will be randomised.

This trial will be conducted across 12 ward bays (6 in each hospital). APCs will be installed next to each bed in the ward.

Running alongside the trial will be mixed methods implementation studies. These will include exploratory research interviews and usability testing in the pilot phase and process evaluation during the main RCT stages.

STOP-GO Criteria

Each trial is due to complete within 6 months, with a 3-month buffer to deal with unforeseen problems.

STOP CRITERIA:

1. The pilot phase for the first trial in consulting rooms will recruit 20% of the patients in 5 weeks.

The trial will STOP if we don't recruit 60% of expected number (i.e. 12% of the total recruitment).

a. Management:

The trial team will report to the trial management group (TMG) at the end of week 5. If recruitment is inadequate, TMG will discuss with the trial team why recruitment failed and explore ideas to improve recruitment before deciding on whether to restart. Discussions may also be had with our programme PPIE panel. The trial will restart if TMG confident it can complete recruitment within 9 months.

2. AISaT tool may not be able to compute a solution to reduce aerosol transmission in the rooms we wish to use for trial.

a. Management: The TMG will allow an extra 3 months to find rooms that the tool can be used in. If we cannot find suitable clinic rooms, TMG will stop the trial.

3. A report will be produced by engineering team at end of pilot on numbers of aerosol droplets measured. Trial statisticians will ensure it will be possible to determine statistically whether the trial could reach predefined end points. If not, TMG will discuss with engineering team how to seed the room with more droplets and then implement. Although unlikely that doctors or patients will notice changes, we will perform a further pilot. TMG will stop second trial if we cannot recruit adequately during pilot as above.

4. Statistical report at the end of the pilot will identify variance in aerosol droplet concentrations between consulting rooms. Even apparently identical rooms may have different airflows. If current sample size inadequate to achieve statistical power needed, statisticians will advise the TMG of a new sample size. TMG to discuss with trial team extra patient recruitment. If unachievable within 9 months, TMG will stop trial.

5. At the end of pilot, trial team will also ask hospital staff whether AI generated mitigations interfere with clinic, procedure room or ward e.g. due to noise or trip hazards. TMG will discuss with engineering team adjusting AISaT system. If not achievable, trial will be stopped.

6. Ensuring adequate research support staff to run trials. This is costed in SoeCAT. We know that NHS Trusts are under pressures and may not have research staff available to enable recruitment. If recruitment in pilot phase is too low, TMG will decide whether to stop the trial at that point.

7. For trial stage 2, based in procedure rooms, issues 1-6 remain relevant. Ventilation rates are higher than in standard consulting rooms, and there is more movement of people as well as intermittent aerosolising equipment use and use of personal protective equipment (PPE) by staff. All these factors may increase standard deviation in aerosol droplet levels. Study sample size may therefore need to be larger, but we will apply the same stop/go criteria as for trial stage 1.

8. All issues above remain relevant in the ward trial stage 3. Here operational risks are key. Ward changes happen for many reasons and are impossible to predict. If a change to wards is needed, the statisticians will advise whether this will impact on trial delivery. If not possible to complete within the time frame, TMG will decide whether to stop the trial.

Duration of Participation in the Trial

For most participants who are only taking part in the clinical trials in pilot phases, stage 1 and 2, participation will be limited to one day for patients (the day they attend clinic), whereas for clinicians it will be 3 weeks. In the ward trial in stage 3, both patient and clinician participation will be for 3 days.

For the small number of participants who are invited to take part in the process evaluation work, participation will be until all interviews are completed. This may take up to 4 months.

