	
per clinical encounter as measured by an air particle counter (APC) installed next to the clinician and at up to 4 other fixed locations in the room or ward bay.
 
In Stage 3 of the RCT, the same three configurations described above will be arranged in 12 ward bays (6 in each hospital), each for one day, in random order. Here, the clinician making the decision for configuration 3 will be the senior nurse for the ward.
 
Running alongside all stages of the trial will be a mixed methods evaluation. This will include usability testing and exploratory research interviews with a subset of clinicians, patients and other relevant hospital staff such as nurses, estates staff and infection prevention and control (IPC) staff in the pilot phase, and a process evaluation during the main RCT stages.

Trial duration per participant:	
Clinicians: 3 weeks
 
Patients in outpatient clinic/ having an AGP: 1 day
 
Ward patients and clinicians: 3 days
 
For those patients or staff involved in the mixed methods evaluation, trial duration will last no more than 4 months.

Key Study milestones:	
Each trial is due to complete within 6 months, with 3 months as a buffer to deal with any unforeseen issues.
 
Month 3: Completion of first pilot phase
 
Month 9: Completion of first clinical trial in outpatient consulting rooms
 
Month 12: Completion of second pilot phase
 
Month 18: Completion of 2nd clinical trial in AGP rooms
 
Month 21: Completion of third pilot phase
 
Month 27: Completion of 3rd clinical trial in ward bays/ Data envelope analysis completed
 
Qualitative and quantitative data collection for the process evaluation will run alongside the clinical trials and will also be complete by month 27.

Estimated total trial duration:	
Anticipated start date: 1st July 2025
 
Anticipated end date: 30th September 2027

Planned trial sites:	
Multi-site:
 
 1. UCL Hospitals NHS Foundation Trust 2. Lister Hospital (East and North Hertfordshire NHS Trust)
Total number of participants planned:	
Stage 1 Pilot: Outpatient clinic rooms
 
12 sessions
 
Up to 12 clinicians

10 patients + 5 accompanying persons each per clinic = 120 patients + 60 accompanying persons = 180 + 12 clinicians

Total = 192

Stage 1: Outpatient clinic rooms

27 clinicians x 2 hospitals = 54 clinicians

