10 patients + 5 accompanying persons per clinic = 540 patients + 270 accompanying persons x 3 weeks = 2430:

Total = **2484**

Stage 2 Pilot: AGP Procedure Rooms

9 sessions

Up to 9 clinicians

10 patients per session per clinician = 90 patients

Total = **99**

Stage 2: AGP Procedure Rooms

27 clinicians x 2 hospitals = 54 clinicians

10 patients per session per clinician = 540 patients x 3 weeks = 1620

Total = **1674**

Stage 3 Pilot: Wards

3 days

Approximately 6 beds in 1 bay. As days may not be consecutive, aim for up to 18 patients

Day nurse & night nurse = 2 per day so **6** in 3 days

Day HCA and night HCA = 2 per day so **6** in 3 days

Up to 3 doctors per day = **9** in 3 days

Total = **18+6+6+9 = 39**

Stage 3: Wards

Each of the 2 hospitals has 6 bays, each bay containing 6 beds. This gives a total of 72 beds.

25% patient turnover rate (72×1.25) = approximately **90** patients in 3 days.

Day nurse & night nurse = 12 per 24 hour period, so **36** in 3 days

Day HCA and night HCA = 12 per 24 hour period, so **36** in 3 days

6 doctors per day = **18** in 3 days

Total = **90+36+36+18= 180**

For each stage, we will also speak to **up to 30** other staff members including estates, infection prevention and control, managers and other relevant staff groups in each hospital. We will conduct

	
ethnographic observations, and informal interviews with infection control leads, clinical and estates staff to consider use of ventilation devices, how they are deployed, how are they used, challenges and solutions to their use - and we will perform up to 15 semi-structured interviews with management leads, clinical and estates staff. With observations.
 
Total = 30 x 2 hospitals x 3 stages = 180
 
Overall total = 192+2484+99+1674+39+180+180= 4848 participants

Inclusion criteria:	
Clinicians working at relevant clinical testing environments (1st trial outpatient clinic room, 2nd trial AGP room, 3rd trial ward bay)
 
All patients (and accompanying persons) attending in those relevant clinical testing environments
 
The mixed method evaluation may include people working in estates teams, hospital managers and other healthcare staff.

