10.4 Planned recruitment rate

Two hospitals are recruiting to this study. The crucial participants to recruit for the first pilot and trial stage 1 is 27 clinicians in each hospital who perform outpatient consultations or aerosol generating procedures (AGPs). Of these, 12 will take part in both the pilot and the stage 1 trial. UCLH has a clinical staff of many thousands and sees 1,800,000 out-patients each year. This equates to around 200,000 separate clinic sessions in multiple clinical areas and there are many dozens of clinical consulting and AGP rooms throughout the estate. The Lister Hospital also has over 2,000 clinical staff and sees 800,000 outpatients each year (around 90,000 separate clinic sessions) and also has multiple clinical areas available. The PI at each site will engage local clinical colleagues, managers and clinical directors to support the work and clinicians who are expected to be in clinic for 3 weeks consecutively will be targeted for recruitment. We expect a dropout rate of around 5% as clinicians must give a minimum of 6 weeks' notice to cancel a clinic, so it is expected that the vast majority of clinicians who agree to take part will attend the relevant clinic sessions.

Recruitment is anticipated to be 10 clinicians per month for stage 1 and its pilot. For stage 2 (and its pilot), 54 clinicians will again be needed. Some of these may be the same ones who participated in stage 1. Recruitment is again anticipated to be 10 clinicians per month. The PI at the Lister Hospital and the CI, who works at UCLH, are both active clinicians who work in outpatients and AGP rooms. This should make recruitment of their clinical colleagues relatively straightforward. The dropout rate is again around 5% as described above.

Of patients attending these clinics and AGP sessions, almost 100% will be eligible and all of these will be invited to take part in the studies (we will not recruit in paediatric, obstetric or psychiatric clinics). Recruitment of patients is therefore likely to be around 300 with approximately 150 accompanying persons per month in both trial stages 1 and 2. Patients will either accept and enrol in the trial, or will not. If they accept and enrol, we do not expect drop-outs. If there were to be, this should have no major impact on the trial endpoints as we will be able to control for this in the data analysis phase. For a 4-hour clinical session, we expect to have 3 hours of analysable data approximately.

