10.10 Sensitivity and other planned analyses

At the end of the clinic, a member of the research staff will ensure that there was compliance to the randomised setting and a log will be kept in order to track this data. The measurements will be reviewed for reliability.

At the end of each pilot phase, an interim statistical analysis will be performed to assess whether the main study is likely to meet the study goals.

Data analysis will be linear mixed modelling of the data controlling for confounding factors. Sensitivity analyses will remove measurements that are considered potentially, or definitely, unreliable. These analyses will be compared to the analyses that keep all collected data points. Interpretation of the main findings

Full data analysis will be undertaken by our co-I at CCTU and his team at the end of each stage of the clinical trials and will again perform data analysis using linear mixed modelling of the data (3 conditions for each clinician) controlling for confounding factors.

Decision criteria used to judge the interim results as part of a guideline for early stopping

Each trial is due to complete within 6 months, with a 3 month buffer to deal with unforeseen problems. The pilot phase for the first trial in consulting rooms will recruit 20% of the patients in 5 weeks. The trial will STOP if we don't recruit 60% of expected number (i.e. 12% of the total recruitment).

The AlSaT tool may not be able to compute a solution to reduce aerosol transmission in the rooms we wish to use for trial. If this occurs, the TMG will allow an extra 3 months to find rooms that the tool can be used in. If we cannot find suitable clinic rooms, TMG will stop the trial.

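### The Stage 1 pilot STOP limit (12% of total recruitment) exceeds the 7.4% that a fully recruited pilot would supply, and Stage 2 inherits the mismatch

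*Protocol*

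**What the plan says.** **The rule.** Protocol section 4, STOP-GO Criteria, item 1: "The pilot phase for the first trial in consulting rooms will recruit 20% of the patients in 5 weeks", followed by "The trial will STOP if we don't recruit 60% of expected number (i.e. 12% of the total recruitment". Section 10.10 repeats it under the guideline for early stopping, with the same gloss: "i.e. 12% of the total recruitment".

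**The pilot's size.** Section 4, Pilot Phase: "In total, a maximum of 12 clinic sessions will be included in consulting rooms in the pilot phase". This is up to four sets of conditions, each run three times. The Study Summary (total number of participants planned) gives "10 patients + 5 accompanying persons each per clinic = 120 patients + 60 accompanying persons = 180 + 12 clinicians".

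**The main trial's size.** The Study Summary gives Stage 1 as "10 patients + 5 accompanying persons per clinic = 540 patients + 270 accompanying persons x 3 weeks = 2430", to which 54 clinicians are added. Section 10.4 says of the clinicians needed: "Of these, 12 will take part in both the pilot and the stage 1 trial".

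**What follows a STOP.** Sections 4 and 10.10 send the recruitment report to the TMG at the end of week 5. The TMG looks for causes and remedies, and the trial restarts if it is confident that recruitment can finish within 9 months.

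**Later stages.** Section 4, item 7, applies the same stop/go criteria to Stage 2. Item 8 says only that the issues already listed stay relevant to Stage 3. The Study Summary plans 90 pilot patients against 1,620 in Stage 2, and up to 18 against about 90 in Stage 3.

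**The concern.** The limit is a share of total recruitment, but the pilot is a separate and much smaller exercise than the stage it precedes. If the largest planned pilot is below the limit, the rule gives the same answer whether recruitment goes perfectly or badly.

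This is the first STOP criterion in the list and the only one with a numerical limit. Section 10.10 relies on adaptations being fixed in advance to protect the trial's integrity. With a limit that the planned pilot cannot meet, the TMG would have to decide at week 5, with the recruitment already known, which number was meant.

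**Working it through.** **Inputs**
- Pilot: at most 12 sessions (section 4), 10 patients each, so 12 x 10 = 120 patients. Adding 60 accompanying persons and 12 clinicians gives 192 (Study Summary).
- Stage 1: 540 x 3 = 1,620 patients and 270 x 3 = 810 accompanying persons, together 2,430. With 54 clinicians this is 2,484.
- Sessions in Stage 1: 54 clinicians x 3 weeks = 162.

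**The plan's own figure.** 0.60 x 0.20 = 0.12, so the 12% follows from the 20%. The 20% does not follow from the pilot's size:
- 20% of 1,620 = 324 patients.
- 12% of 1,620 = 194.4, so 195 patients are needed to avoid STOP.
- Full pilot: 120/1,620 = 7.4%. The shortfall is 195 - 120 = 75 patients.

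**Other denominators**

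| Base | Full pilot / total | Share | Meets 12%? |
|---|---|---|---|
| Patients, Stage 1 | 120/1,620 | 7.4% | no |
| Patients, pilot + Stage 1 | 120/1,740 | 6.9% | no |
| Patients + accompanying persons | 180/2,430 | 7.4% | no |
| All Stage 1 participants | 192/2,484 | 7.7% | no |
| All participants, pilot + Stage 1 | 192/2,676 | 7.2% | no |
| Whole programme | 192/4,848 | 4.0% | no |
| Sessions | 12/162 | 7.4% | no |
| Clinicians | 12/54 | 22.2% | yes |
| One week's patients | 120/540 | 22.2% | yes |

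Only the last two rows reach 12%, and the rule names neither base.

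**Dependence on 10 patients per clinic.** Against a fixed 1,620, the limit would need 194.4/12 = 16.2 patients per session, or 194.4/10 = 19.4, so 20 sessions. If clinic size changed in the pilot and in Stage 1 alike, the session ratio would still be 7.4%.

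**Limits the pilot can reach**
- 60% of the pilot's own 120 patients: 72 (72/1,620 = 4.4% of Stage 1).
- Clinicians: 20% of 54 = 10.8, about 11; 12% of 54 = 6.48, so 7.

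**Later stages**
- Stage 2: 90/1,620 = 5.6%, below 12%. 60% of 90 = 54 patients.
- Stage 3: 18/90 = 20%, exactly the stated share. 12% of 90 = 10.8, so 11 patients, which is reachable.

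**The case against.** **STOP is not the end of the trial.** A reader might infer that the rule ends the trial with certainty. The documents do not support that. STOP leads to TMG review with a stated restart test; item 6 of the criteria also leaves low pilot recruitment to the TMG's judgement, and section 10.10 gives final authority to the trial steering committee. This stands. The restart test, however, is a matter of confidence about future recruitment. It does not repair a limit that a pilot run to plan cannot meet.

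**The unit word may be the error, not the percentages.** Section 10.4 treats clinicians as the crucial recruits and expects 10 per month for Stage 1 and its pilot. Five weeks at that rate is 10 x 12 x 5/52 = 11.5, or 21% of 54, and 12 of 54 is 22%. The clinician reading thus fits both the pilot's size and the five weeks. It is at least as plausible as the other explanation, that the 20% came from the main-trial patient rate (300 x 12 x 5/52 = 346, or 21% of 1,620). The protocol does not settle which was intended. As written it says patients.

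**Patients are a legitimate thing to count.** Section 5.3 excludes data from the time when a non-consenting patient is in the room, and section 10.8 requires a session with under 2 hours of data to be repeated. Patient uptake is therefore a fair feasibility measure, and the choice of unit is not itself a fault.

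**The rule is operational.** It does not touch the primary outcome, randomisation, error rate or power. That stands, and it bounds the consequence.

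**Conclusion.** The point holds for Stages 1 and 2. The stated limit needs 195 patients and the planned Stage 1 pilot supplies at most 120: 7.4% against 12%, with a range of 6.9% to 7.7% over the Stage 1 denominators for patients and participants. A pilot recruited fully as planned triggers STOP, so the criterion carries no information about recruitment. The practical effect is an automatic TMG review and an undefined choice among limits as far apart as 72 patients, 195 patients and 7 clinicians.

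This rests on the planned 10 patients per clinic, the 12-session cap, and reading patients and total recruitment in their ordinary sense.

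A reader might also extend the point to Stage 3. The figures do not support that: the Stage 3 pilot plans up to 18 of about 90 patients, which is the stated 20%.

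**What to change.** In sections 4 and 10.10, state one denominator that the pilot can reach, and settle it before pilot recruitment is reviewed. Either would do:

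- **Patients.** Set the limit at 60% of the patients planned for the pilot sessions actually scheduled: 72 of 120 if all 12 run. Tie it to scheduled sessions because 12 is a maximum, not a target. If two sets of conditions proved enough, 6 sessions would be scheduled and the limit would be 36 of 60.
- **Clinicians.** If clinicians were meant, say so. The existing percentages can then stay, with the counts written in: about 11 of 54 expected, and a limit of 7 of 54.

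Give Stage 2 its own matching count, for example 54 of 90 patients. If clinicians are chosen, the Stage 2 expected share also needs restating, since its pilot has up to 9 clinicians (9/54 = 16.7%, above 12% but below 20%). For Stage 3, say whether the rule applies.

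The cost is a few sentences in a protocol amendment, with no extra participants and no change to the analysis.

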10.3 Sample size calculation

Participants: 3 consulting rooms or 3 AGP rooms in each hub hospital. 54 clinicians who regularly use these rooms (27 per hospital approximately) will be invited to take part, each for 3 consecutive weeks.

A 3-period, 3-treatment cross-over design will be used to test whether there is a difference in the 3 means. The comparison will be made using a Geisser-Greenhouse corrected F-test with a Type I error rate (α) of 0.05. The group means under the null hypothesis are assumed to be equal. The standard deviation across subjects at the same period is assumed to be 1 (and the means are expressed, see below, as a fraction of the standard deviation, which allows us to calculate a sample size using the Cohen's D approach). The assumed pattern of the covariance matrix is 'all correlations equal' (compound symmetry) with a correlation of 0.5 between adjacent time point measurements. To detect group means of '0 0.25 0.5' with 90% power, the needed number of clinicians is 53 (each measured 3 times). Given that there are six possible sequence combinations of the 3 treatments, the sample size is increased to the closest multiplicator of 6, which is 54. The sample size was computed using PASS 2024, version 24.0.2.

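### The pilot's sample-size check expects a droplet SD to move a sample size set in SD units, reports between-room instead of within-clinician variance, and names patients where the calculation counts clinicians

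*Protocol*

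**What the plan says.** **Sample size (protocol 10.3).** The test is a "Geisser-Greenhouse corrected F-test with a Type I error rate (α) of 0.05". The SD is set to 1 by assumption. As to the effect, "the means are expressed, see below, as a fraction of the standard deviation". Correlations are taken as equal at 0.5. For 90% power to detect means of 0, 0.25 and 0.5, the section gives 53 clinicians, raised to 54 so that the six sequences divide evenly. It gives no difference in droplets per minute, absolute or relative. Nor do the primary objective (3.1) and the primary outcome (3.3, 10.1).

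**Pilot check (section 4, stop-go item 4).** "Statistical report at the end of the pilot will identify variance in aerosol droplet concentrations between consulting rooms". Then: "If current sample size inadequate to achieve statistical power needed, statisticians will advise the TMG of a new sample size". The remedy is "TMG to discuss with trial team extra patient recruitment", and the trial stops if this cannot be done within nine months. Section 10.10 repeats the rule, with clinical areas in place of consulting rooms.

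**Stage 2 (stop-go item 7).** Several features of procedure rooms are expected to raise the SD of droplet levels, and the inference drawn is "Study sample size may therefore need to be larger".

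**Design (section 4).** Clinicians are randomised and patients are not. Each clinician is their own control and holds weekly sessions in the same rooms.

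**The concern.** Items 4 and 7 reason that a noisier room needs a larger trial. That is right only if the difference to be detected is fixed in droplets. In 10.3 it is fixed in SDs, so when the SD grows the target grows with it and the required number stays put. Read together, the passages leave the statisticians no stated route from a pilot SD to a new sample size.

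Two further mismatches lie in the same rule. The reported variance is one that a within-clinician comparison largely removes, and the remedy is given in a unit that the calculation does not count.

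At stake is a decision rule that can enlarge or stop the trial. Followed as written, it could pass a noisy setting whose smallest detectable droplet reduction has grown unnoticed, or raise an alarm over room differences that do little to the comparison.

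**Working it through.** **Inputs (all from 10.3):** α = 0.05, overall F-test on three means; SD = 1; means 0, 0.25, 0.5; correlation ρ = 0.5, compound symmetry, so the Geisser-Greenhouse factor is 1.

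**Step 1. Reproduce the plan's figure.** The noncentrality is λ = n·Σ(μ − mean)² / [SD²(1 − ρ)], with 2 and 2(n − 1) degrees of freedom. Here Σ(μ − mean)² = 0.0625 + 0 + 0.0625 = 0.125, so λ = 0.125n/0.5 = 0.25n. Power is 0.899 at n = 52, 0.905 at 53 and 0.911 at 54. The stated 53 is reproduced exactly.

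**Step 2. Change the SD and keep the target in SD units.** With means 0, 0.25·SD and 0.5·SD, the SD cancels from λ. For an SD of 1, 10, 100 or 1000 the answer is 53 each time.

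**Step 3. Change the SD and keep the target fixed on the droplet scale.** This is an illustration. It assumes that 0/0.25/0.5 is a fixed difference in units of the planned SD, with ρ = 0.5, so λ = 0.25n/s², where s is the ratio of the actual SD to the planned SD.

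| s | λ at n = 54 | Power at 54 | Clinicians for 90% |
|---|---|---|---|
| 1 | 13.50 | 91% | 53 |
| 1.25 | 8.64 | 74% | 81 |
| 1.5 | 6.00 | 57% | 116 |
| 2 | 3.38 | 35% | 204 |

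**Step 4. Which variance matters.** Split SD² into a between-clinician/room part and a within-clinician part, SD²(1 − ρ). The plan's inputs give 0.5 each. Keep the fixed target of step 3 and assume additive room effects with each clinician staying in one room.

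- Within part held at 0.5, between part raised from 0.1 to 4: n stays at 53.
- Between part held at 0.5, within part 0.25, 0.5, 0.75, 1.0, 2.0: n = 27, 53, 78, 103, 204.

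If between-room variance were instead fed in through ρ with the target left in SD units, n would fall as rooms differ more. Raising the between part from 0.5 to 2 (ρ from 0.5 to 0.8) takes n from 53 to 22, the opposite of what item 4 intends.

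**Step 5. The correlation.** With the target in SD units, ρ does move n: 73 at 0.3, 63 at 0.4, 53 at 0.5, 43 at 0.6, 32 at 0.7. The protocol does not say that the pilot will estimate it.

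**Step 6. What the stage 1 pilot can supply.** Section 4 allows at most 12 sessions (up to four aerosol conditions, three times each). The study summary lists up to 12 clinicians, and 10.4 has 12 clinicians in both pilot and stage 1, which points to one session each. The duration paragraph of section 4 covers the pilot phases and gives clinicians three weeks, which points to repeats. If three clinicians each took four conditions, the residual df would be (3 − 1)(4 − 1) = 6. The 95% limits for the SD would be √(6/14.45) = 0.64 to √(6/1.24) = 2.20 times the estimate. An estimate equal to the planning value would be compatible with n from 23 to 247.

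**The case against.** **The pilot could still inform n.** A reader might infer that nothing found in the pilot can alter the sample size. The documents do not support that. The correlation is an input and moves n (step 5). An SD of 1 is also only a planning assumption: item 3 and 10.10 ask the statisticians whether the end points are reachable, and they could compare pilot droplet levels with the assumed pattern. This stands, but the rule as written names neither the correlation nor any droplet value to compare with.

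**Between-room variance is not irrelevant.** It cancels only if room effects are additive and each clinician keeps one room. AISaT is tailored to the room (6.1), and section 2 says that device performance depends heavily on location and airflow. If mitigation helps more in some rooms than in others, that room-by-configuration variation does not cancel. So the between-room figure is insufficient, but it has some use.

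**Pilot repeats are not excluded.** A reader might conclude that each pilot clinician has a single session and that within-clinician variance is therefore inestimable. That is the likelier reading of the study summary with 10.4, but it is not stated, and the duration paragraph points the other way.

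**Extra patients may help a little.** Suppose all within-clinician noise were between encounters. On the fixed target of step 3, going from 10 to 15 patients per session would then lower n from 53 to 36. If it is all between sessions, n stays at 53. The documents give no split. Sections 10.3 and 10.4 do make clear that clinicians are the sample, so the remedy may be loose wording; it still needs correcting in a rule that can stop the trial.

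**The method may be in the SAP.** Details of a re-estimation could be. The target scale, the variance, the remedy and the stop rule are fixed in the protocol, and they do not fit one another.

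**Conclusion.** The point holds. The stated 53 is correct for its inputs, and nothing here affects the type I error or the validity of the estimates. What fails is the safeguard: with a target in SD units a larger pilot SD alone cannot change n, so items 4 and 7 and section 10.10 rest on an assumption that 10.3 does not meet. The variance they report is not the main driver of precision, and the remedy is in the wrong unit.

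The power losses in step 3 are conditional. They assume a fixed droplet difference equal to today's pattern, a correlation of 0.5, and SD inflations chosen for illustration, since the documents give no droplet SD. They should not be read as a forecast that the trial is underpowered.

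**What to change.** 1. Before any pilot data are seen, state in 10.3 the target as a fixed droplet reduction for the AISaT contrasts (absolute, or relative on the log scale).
2. In stop-go item 4 and in 10.10, base the check on the within-clinician, session-to-session SD and the correlation of droplets per minute on the analysis scale. Keep between-room variance as a descriptive result.
3. Replace the patient-recruitment remedy with recruitment of additional clinicians.
4. Reconcile the statements on pilot clinicians in the study summary, section 4 (pilot phase and duration of participation) and 10.4, and have some clinicians repeat within the planned sessions.
5. Say that the pilot estimate is not definitive and that a cautious upper value of the SD will be used.

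The cost is protocol wording, one agreed target figure and a pilot rota within the sessions already planned. Planning on an upper value may call for more clinicians than 54. That follows from the small pilot, and a change of rota alone will not remove it.
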